**Funder**

This study is funded as part of a Wellcome Trust Research Fellowship held by [name].

This protocol describes the AIM-Skin study and provides information about procedures for entering participants. The protocol should not be used as a guide for the treatment of other participants; every care was taken in its drafting, but corrections or amendments may be necessary. These will be circulated to investigators in the study, but centres entering participants for the first time are advised to contact the trials centre to confirm they have the most recent version.

Problems relating to this trial should be referred, in the first instance, to the study coordination centre.

This trial will adhere to the principles outlined in the International Conference on Harmonisation Good Clinical Practice (ICH GCP) guidelines, protocol and all applicable local regulations.

## **GLOSSARY OF ABBREVIATIONS**

AAH	Atoifi Adeventist Hospital
AE	Adverse Event
MDA	Mass Drug Administration
SAE	Serious Adverse Event
SUSAR	Serious Unexepected Event

## **KEYWORDS**

Yaws  
Scabies  
Azithromycin  
Ivermectin  
Impetigo  
MDA

## STUDY SUMMARY

**TITLE** Impact of Single-Dose Azithromycin in Impetigo and Skin Microbiology

**DESIGN** A prospective community intervention trial to assess the impact of community mass treatment with azithromycin for yaws and ivermectin for scabies, on non-yaws bacterial skin infections.

**AIMS** Assess the impact of single dose azithromycin, given for yaws, on other prevalent bacterial skin infections.  
Assess the impact of single dose azithromycin on antimicrobial resistance patterns in isolates of *S.pyogenes* and *S.aureus*.

**OUTCOME MEASURES** Primary Outcome  
a) Difference in the change in prevalence of impetigo between baseline and 12-months between the parallel and the sequential treatment arms.

Secondary Outcomes  
b) Change in the proportion of swab samples from which *S. pyogenes* is cultured between baseline and follow-up in the two arms  
c) The proportion of samples from which a drug-resistant isolate of *S.pyogenes* is cultured in the two arms

**POPULATION** Parallel Treatment Arm: Sample size of 637  
Sequential Treatment Arm: Sample size of 637

**ELIGIBILITY** All residents of selected communities are eligible to participate in the study

**TREATMENT** *Treatment of yaws:*  
Single dose of Azithromycin (30mg/kg, max 2G).

*Treatment of scabies:*

Either an oral dose of Ivermectin (200µg/kg) or permethrin cream for those with a contraindication to Ivermectin (WT<15kg, pregnant or breastfeeding women) given in 2 doses 7-14 days apart.

**DURATION** 12 months

## **1. INTRODUCTION**

### **1.1 BACKGROUND**

Both trachoma, caused by *Chlamydia trachomatis*, and yaws, caused by *Treponema pallidum* subsp. *pertenue*, are endemic in many Pacific countries including the Solomon Islands[1,2]. Mass treatment with azithromycin is the cornerstone of the WHO strategy for the elimination and eradication of these two diseases respectively[3,4]. Mass treatment with azithromycin has been shown to have beneficial off-target effects including decreased malaria transmission and some evidence to support a reduction in infant mortality [5,6]. Conversely, mass treatment with azithromycin has been associated with changes in the resistance patterns of nasopharyngeal isolates of *Streptococcus pneumoniae*[7].

Scabies is also a significant public health problems in the Pacific[8]. Scabies is associated with secondary bacterial infections (impetigo) which are most commonly caused by *Streptococcus pyogenes* and *Staphylococcus aureus*[9]. Recently community mass treatment with Ivermectin has been shown to be an effective strategy for reducing the prevalence of both scabies and associated bacterial complications[10]. Recent surveys conducted in the Solomon Islands have shown that the prevalence of scabies is between 18-25% and the prevalence of impetigo between 25-40% ([name], personal communication).

### **1.2 RATIONALE FOR CURRENT STUDY**

Current WHO recommendations for yaws are for community mass treatment with single dose azithromycin[3]. The impact of this treatment on other bacterial skin diseases is unknown.

Azithromycin has activity against both *S. pyogenes* and *S. aureus* and mass treatment with azithromycin, for either yaws or trachoma control, might have additional impacts on both the prevalence of impetigo and the potential emergence of resistant organisms. These issues may be of particular relevance in the Pacific where mass treatment for yaws or trachoma is likely to be conducted in the near future and where scabies and impetigo are also both common.

Understanding the impact of azithromycin mass treatment on impetigo will inform whether integrated control programmes for yaws, trachoma and scabies could be considered in the Pacific where all three diseases are endemic.

## 2. STUDY OBJECTIVES

### Study Aims:

Assess the impact of single dose azithromycin, given for yaws, on other prevalent bacterial skin infections.

Assess the impact of single dose azithromycin on antimicrobial resistance patterns in isolates of *S.pyogenes* and *S.aureus*.

### Primary Objective:

The primary objective is to see whether a single dose of azithromycin, given as treatment for yaws, has an additional impact on impetigo.

### Secondary Objectives:

The secondary objective is to assess whether treatment with a single dose of azithromycin results in change in the anti-microbial susceptibility of clinical skin swab isolates .

### 3. STUDY DESIGN

This is an open-label prospective community intervention trial to assess the impact of community mass treatment with azithromycin for yaws and ivermectin for scabies, on non-yaws bacterial skin infections.

[figure not shown]
#### Study Site

This study will be conducted within communities residing in the catchment area of Atoifi Adventist Hospital (AAH), Malaita Province, Solomon Islands. Both yaws and scabies are known to be endemic across the whole of the Solomon Islands[1].

#### Duration

The duration of the study is 12 months. For all participants, there will be a 15 day on-study period which will include two visits by the study team

- Day 1 for baseline medical assessment and delivery of azithromycin/tetracycline and ivermectin/permethrin
- Day 8-15 for delivery of second dose of ivermectin/permethrin

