### *Site 2- Serial Treatment Arm*

Ivermectin/Permethrin (for scabies) will be offered on D1 with a second dose of Ivermectin/Permethrin offered 7-14 days later..

Single dose azithromycin (for yaws) will be offered at the twelve month follow-up visit.

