#### 7.3.1 Non serious Adverse Reactions (ARs)/Adverse Events (AEs)

Given the established safety profile of the drugs being used in this study and the fact that they are being used for established indications we will only collect data on SAEs and SUSARs.

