#### 7.3.2 Serious Adverse Reactions (SARs)/Serious Adverse Events (SAEs)

Serious Adverse Events (SAEs) and Serious Adverse Reactions (SARs) should be reported to the study coordination centre within 24 hours of the local site being made aware of the event.

An SAE form should be completed and submitted to the study coordination centre with as much detail of the event that is available at that time. If awaiting further details, a follow up SAE report should be submitted promptly upon receipt of any outstanding information. The CI (for a single-centre trial) or PI (for a multi-centre trial) must record the event with an assessment of seriousness, causality and expectedness.

Any events relating to a pre-existing condition or any planned hospitalisations for elective treatment of a pre-existing condition do not need reporting as SAEs.

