### Follow-Up Data Collection

At follow-up all individuals will undergo again undergo a standardized examination to collect data on the presence of skin lesions consistent with yaws, scabies and impetigo. Following examination a finger-prick sample will be obtained from all individuals on to filter paper. In individuals with skin lesions consistent with yaws the same finger prick sample will be used for a rapid diagnostic test for yaws. In individuals with skin lesions consistent with yaws the same finger prick sample will be used for a rapid diagnostic test for yaws. In individuals with skin lesions consistent with yaws or impetigo two sterile lesion swabs will be obtained.

In communities where azithromycin mass treatment was not conducted at baseline (sequential treatment arm 2) this will be offered at the follow-up visit.

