### **8.2 TRIAL CLOSURE**

The trial is planned to run over a 12 month period. The trial will be complete at the end of this 12 month period. SEP

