## **10. MONITORING**

### **10.1 RISK ASSESSMENT**

This is considered a low risk study.

All the drugs being used are being prescribed for routine indications and have well established safety profiles. As such only passive monitoring for adverse events will be undertaken during the study.

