### **10.3 MONITORING AT LOCAL SITE**

Site visits will take place at D1 (treatment for yaws and scabies), D8 (second treatment for scabies) and month 12 (assessment of outcome).

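### The sequential arm is offered azithromycin at the month-12 visit, when the trial is planned to end, so about 47% of planned azithromycin doses have no assured SAE reporting period afterwards

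*Combined protocol and SAP*

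**What the plan says.** **Dosing.** The Site 1 description gives the parallel arm azithromycin on Day 1, together with the first scabies dose. Under Site 2, "Single dose azithromycin (for yaws) will be offered at the twelve month follow-up visit". The Follow-Up Data Collection part of section 8 repeats this: "In communities where azithromycin mass treatment was not conducted at baseline (sequential treatment arm 2) this will be offered at the follow-up visit".

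**Study period.** The Duration section sets a 12-month study and adds: "For all participants, there will be a 15 day on-study period which will include two visits by the study team". The two visits listed are Day 1 and Day 8-15. Section 8.2 states: "The trial will be complete at the end of this 12 month period". Section 11.1 ties the end-of-study notification to the one-year duration. Section 10.3 lists site visits at Day 1, Day 8 and month 12, and labels the last as outcome assessment.

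**Safety data.** Section 7.3.1 limits collection: "we will only collect data on SAEs and SUSARs". Under section 7.3.2, SAEs and SARs "should be reported to the study coordination centre within 24 hours of the local site being made aware of the event". Section 10.1 says: "As such only passive monitoring for adverse events will be undertaken during the study". Section 12 appoints no DSMB. No section states how long after a dose an SAE remains reportable.

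**The concern.** SAE and SUSAR reports are the only safety data that the trial collects, and no DSMB looks at them. The protocol does not limit that collection by arm. Yet the rules on dose timing, closure and monitoring combine so that one arm takes azithromycin near the start of a year of open reporting, and the other takes it as the study closes. Section 6.1 gives azithromycin a plasma terminal half-life of 2-4 days, so people dosed at the last visit still carry the drug after the team has left.

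Two things are at stake. First, an SAE in the days after a month-12 dose could go unrecorded because no one is asked to report it. Second, a final SAE count for azithromycin, particularly a count of zero, could be read as covering everyone dosed when nearly half had no defined observation period.

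**Working it through.** **1. What follows each azithromycin dose**

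| | Parallel arm | Sequential arm |
|---|---|---|
| Azithromycin offered | Day 1 | Month-12 visit |
| Later study visits described | Day 8-15, month 3, month 12 | None |
| Time left until planned completion (8.2) | About 12 months | None assured |
| Passive monitoring during the study (10.1) | About 12 months | None assured |
| SAE reporting period stated after the dose (7.3) | None | None |

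The last row is the same in both arms. The difference comes from where the dose falls relative to the end of the study.

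**2. The planned number per arm**

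The study summary gives 637 per arm. Section 9 assumes month-12 impetigo prevalences of 10% and 5%, 90% power, 80% enrolment and 10% loss to follow-up. Alpha is not stated; I assume 5% two-sided.

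- Pooled variance: n = [1.960 × √(2 × 0.075 × 0.925) + 1.282 × √(0.10 × 0.90 + 0.05 × 0.95)]² / 0.05², which gives 582 per arm. Allowing for loss, 582 / 0.9 = 647, within 2% of 637.
- Unpooled variance: n = (1.960 + 1.282)² × (0.09 + 0.0475) / 0.05² = 578. Then 578 × 1.1 = 636, one below 637.
- Adding the enrolment factor: 582 / (0.8 × 0.9) = 809, which does not match.

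So 637 is most plausibly the number enrolled, although section 9 does not say so.

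**3. Share of azithromycin doses given at month 12**

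Let L be the proportion of the sequential arm lost by month 12, and suppose everyone present accepts the dose. With N per arm:

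share = N(1 − L) / [N + N(1 − L)] = (1 − L) / (2 − L)

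| L | Month-12 doses / all doses (N = 637) | Share |
|---|---|---|
| 0% | 637 / 1,274 | 50.0% |
| 10% (planned) | 573 / 1,210 | 47.4% |
| 20% (assumed, for range) | 510 / 1,147 | 44.4% |
| 30% (assumed, for range) | 446 / 1,083 | 41.2% |

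N cancels. If 637 were instead the number before 80% enrolment, the counts would be 637 × 0.8 = 510 and 510 × 0.9 = 459, and 459 / 969 is again 47.4%. The 573 is not a ceiling: it already assumes 10% loss, and the dose is offered to the whole community.

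**4. Length of a suitable window**

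At a half-life of 2-4 days, 14 days spans 14 / 4 = 3.5 to 14 / 2 = 7 half-lives.

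**The case against.** **The cut-off is inferred.** This is the strongest objection. Section 7.3 sets no end date. The 24-hour duty in 7.3.2 starts when the site becomes aware of an event, and nothing cancels it at month 12. A reader might infer that SAEs after the month-12 dose are excluded, or that collecting them is impossible. The documents do not support that: a hospital that learned of such an event could still report it. What stands is that nothing requires or schedules this once the trial is complete.

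**An SOP may set the window.** Section 7.3.3 cites a sponsor SOP on adverse-event handling in IMP studies. It is not available here and could contain a reporting period. The protocol cites it for expedited timescales and does not say that it sets one.

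**The visit schedule proves less than it seems.** The 15-day on-study period describes treatment delivery, so it should not be read as a safety window. Section 10.3 is not exhaustive, since it omits the month-3 visit. A reader might also infer that the parallel arm gets safety checks at Day 8 and month 3. No adverse-event enquiry is described at either visit. The parallel arm's advantage is an open study with further contact; neither arm has active surveillance.

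**The drugs are well known.** Safety is not an objective, azithromycin is standard treatment, and dosing is directly observed, so an immediate reaction would be seen. This justifies passive monitoring and leaving out non-serious events. It does not explain why an SAE commitment made without regard to arm should have assured time after the dose in one arm only.

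**An upper confidence limit for the SAE risk.** It is tempting to compare limits after a zero count with one arm or both arms observed. The documents do not support this. Passive reporting does not give complete ascertainment, communities are clusters, and the parallel arm takes azithromycin together with scabies treatment. The protocol plans no such estimate.

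**Conclusion.** The concern holds as a gap in assured safety collection. On the planned inputs, about 47% of azithromycin doses (573 of 1,210; 50% with no loss) have no assured SAE/SUSAR collection period afterwards, against about 12 months of open passive reporting for the parallel arm's dose.

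This rests on reading section 8.2 together with section 10.1, because no explicit cut-off is written. The share assumes that everyone present takes azithromycin and that loss to follow-up means missing the month-12 dose. It ranges from 41% to 50% for losses of 30% down to none.

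The primary comparison is unaffected: impetigo is assessed at the same visit at which this dose is offered. The point is worth fixing because the remedy is small and SAE reports are the only safety data.

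**What to change.** - **Section 7.3:** state a passive SAE/SUSAR reporting period after each azithromycin dose, the same in both arms. Fourteen days is a reasonable choice and fits the 15-day on-study period that the protocol already uses.
- **Sections 8.2 and 10.1:** for sequential communities, set trial completion at the month-12 azithromycin dose plus that period, and say that passive monitoring continues until then.
- **Section 11.1:** send the end-of-study notification after the period closes.
- **Reporting:** give SAEs after azithromycin by arm, with the number dosed in each.

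The cost is an amendment to both ethics committees and about two more weeks of passive reporting in the sequential communities. No extra visit or active surveillance is needed, and the sample size, primary outcome and month-12 examination stay as they are.

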## Treatment

No investigational medications or indications are being assessed. Both study sites will receive standard treatment for both yaws and scabies either in parallel (site 1) or in sequence (site 2).

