### *Site 1- Parallel Treatment Arm*

Single dose azithromycin (for yaws) and Ivermectin/Permethrin (for scabies) will be offered on D1. A second dose of Ivermectin/Permethrin will be offered 7-14 days later.

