## **5. RANDOMISATION AND ENROLMENT PROCEDURE**

### **5.1 RANDOMISATION OR REGISTRATION PRACTICALITIES**

Randomisation will be done at the level of the community by drawing sealed envelopes. All individuals within a community will be offered treatment in line with the randomisation of that community. All residents of the selected communities will be invited to participate in the study.

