## 9. STATISTICS AND DATA ANALYSIS

### *Sample Size*

The sample size required for our primary outcome was estimated as follows:

- Pre-MDA prevalence of impetigo of 25-30%
- Impetigo prevalence to fall to about 10% in the Ivermectin only arm
- Impetigo prevalence to fall to about 5% in the combined arm
- Enrolment 80%
- Loss to follow-up 10%
- 90% power to detect a difference between the two arms

Primary Outcome:

- a) Prevalence of impetigo at months 12 months in parallel treatment communities compared to sequential treatment communities.

Secondary outcomes:

- b) Change in the proportion of swab samples from which *S. pyogenes* is cultured between baseline and follow-up in the two arms
- c) Proportion of samples from which a drug-resistant isolate is cultured.

Data and all appropriate documentation will be stored for a minimum of 5 years after the completion of the study, including the follow-up period.

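### Arms are labelled as two sites while communities are randomised, the number of communities per arm is not given, and the stated 90% power makes no allowance for community randomisation

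*Combined protocol and SAP*

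**What the plan says.** The protocol describes the allocated unit in two ways.

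- **By site.** Section 3, Treatment: "Both study sites will receive standard treatment for both yaws and scabies either in parallel (site 1) or in sequence (site 2". The arm descriptions that follow are headed "Site 1- Parallel Treatment Arm" and "Site 2- Serial Treatment Arm".
- **By community.** Section 5.1: "Randomisation will be done at the level of the community by drawing sealed envelopes". Section 8, Follow-Up Data Collection: "In communities where azithromycin mass treatment was not conducted at baseline (sequential treatment arm 2) this will be offered at the follow-up visit". Section 9 words the primary comparison as prevalence at 12 months "in parallel treatment communities compared to sequential treatment communities".

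On numbers, the Study Summary gives "Parallel Treatment Arm: Sample size of 637" and the same for the sequential arm. Section 9 lists 12-month prevalences of about 10% and 5%, 80% enrolment, 10% loss to follow-up and 90% power. Section 8.1 acknowledges that the trial is not individually randomised, but the only allowance it names is for loss to follow-up. Communities are called selected ("All residents of the selected communities will be invited to participate in the study") but are not counted. The readable text contains no ICC, between-community CV, design effect or method of analysis.

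**The concern.** In a community-randomised trial, the evidence for a treatment effect comes from comparing communities with communities. The site labels leave open whether an envelope decides each community's arm or whether all communities in one place share an arm. In the second case, anything else that changes impetigo at one site over the year (an outbreak, a health campaign, seasonal movement) cannot be told apart from azithromycin.

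Under either reading, precision depends on the number of communities as well as the number of people. A sample size that counts only people sets no number of communities, so it cannot support a power claim for this design.

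**Working it through.** **1. Reproduce the plan's figure.** Inputs from Section 9: 10% v 5%, 90% power, 10% loss. Alpha is not stated; I assume 0.05 two-sided.

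- Unpooled variance: n = (1.960 + 1.282)² x (0.10 x 0.90 + 0.05 x 0.95) / 0.05² = 10.507 x 0.1375 / 0.0025 = 578. With 10% added, 578 x 1.1 = 636; with division by 0.9, 643.
- Pooled variance: n = 582, and 582/0.9 = 647.
- Also dividing by the 80% enrolment: 582/0.72 = 809, which does not match.

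So 637 is most simply read as the number enrolled, from a comparison of independent individuals. There is no room for a clustering allowance: 637 x 0.9 = 573 analysed, already slightly below 578. Power at 573 per arm is 89.6%, from

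power(n) = Φ{[0.05 − 1.96 √(2 x 0.075 x 0.925 / n)] / √(0.1375 / n)}.

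**2. Allow for communities.** With c equal communities per arm, m = 573/c, the design effect is DE = 1 + (m − 1) x ICC and the effective n is 573/DE. The ICC is my assumption, with a range.

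| ICC | 4 per arm (m = 143.25): DE, effective n, power | 10 per arm (m = 57.3): DE, effective n, power |
|---|---|---|
| 0.005 | 1.71, 335, 69% | 1.28, 447, 81% |
| 0.01 | 2.42, 237, 54% | 1.56, 367, 73% |
| 0.05 | 8.11, 71, 20% | 3.81, 150, 38% |

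These are normal approximations and are favourable with few communities, because they ignore the 2(c − 1) degrees of freedom. A community-level t calculation at an assumed CV of 0.25 gives 52% with 4 per arm and 76% with 10. At 7.5% prevalence that CV corresponds to an ICC of 0.25² x 0.075/0.925 = 0.005, so the figures to compare are 69% and 81%.

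**3. How few communities is too few.** The smallest two-sided p-value of an exact unpaired permutation test with c communities per arm is 2/C(2c, c): 2/6 = 0.33 for two, 2/20 = 0.10 for three, 2/70 = 0.029 for four.

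**4. What change from baseline removes.** Section 3.1 defines the primary outcome as the difference between arms in change from baseline. Subtracting baseline cancels a stable difference between places. It leaves any difference between places in how impetigo moves over the 12 months. If all communities in an arm share a site, that difference stays in the treatment contrast.

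**The case against.** The best defence is that the site labels are loose names for the arms. Section 3, Study Site, describes communities in one hospital's catchment. Section 5.1 draws envelopes by community, Section 8 has the team return to each community, and Sections 8 and 9 use the plural, Section 9 for both arms. Most of this stands.

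A reader might therefore infer from the site labels that the trial has one cluster per arm. The documents do not support that: the plural wording points the other way, and the missing design figure may show the number of communities. What remains is that the plural fixes no number (two or three per arm would also fit it) and that Section 3 still contradicts Section 5.1.

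A reader might also infer that the 90% power has no basis. It has one: 637 follows from the listed assumptions for independent individuals. The fault is that this is not the design described.

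The ICC and CV values are assumptions, and the power figures concern 12-month prevalence, as Section 9 words the outcome. Power for the change from baseline also depends on how stable community prevalence is over time, which the documents do not give; baseline information may reduce the loss.

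Finally, four communities per arm is the floor of one particular test, reached only if the two arms separate completely. A t-test on three community prevalences per arm can give p<0.05. The floor is therefore no sample-size justification, and four per arm with the same 637 people should not be taken as sufficient.

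**Conclusion.** The concern holds as two linked faults: contradictory definitions of the allocated unit with no readable number of communities, and a power statement that makes no allowance for allocation by community.

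Confounding with site is conditional. It arises if arm follows site, and does not if an envelope is drawn for each community regardless of site.

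The power shortfall does not depend on that reading. With any positive ICC and several people per community, power is below the 89.6% obtained for independent individuals. Its size rests on the assumed ICC (0.005 to 0.05), alpha of 0.05 two-sided, equal community sizes and 573 analysed per arm: 20% to 69% with 4 communities per arm and 38% to 81% with 10.

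**What to change.** - In Section 3 (Treatment and the two arm headings), replace the site labels with communities allocated to parallel or to sequential treatment, so that the arm is set by the envelope drawn for each community.
- In Section 5.1, state the number of communities per arm and that equal numbers of envelopes are prepared for each arm.
- In Section 9, restate the power for that number of communities, using a stated and justified ICC or between-community CV, and specify an analysis that accounts for community.
- If there are too few communities per arm to estimate between-community variation (with fewer than four, an exact unpaired community-level test cannot reach p<0.05), withdraw the 90% power claim and report the comparison as descriptive.

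The cost is protocol wording, the envelope draw and possibly some extra travel if the same people are spread over more communities. The stated power will be less favourable. Spreading 637 per arm more widely recovers part of the loss but, on the figures above, does not restore 90% with 10 communities per arm; keeping 90% could require more communities or more participants.
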